10.1.4 FOLLOW-UP OF AES AND SAES

After the initial AE/SAE report, the Investigator is required to proactively follow each participant and provide further information to the Sponsor on the participant's condition. All AEs and SAEs documented at a previous visit/contact and are designated as ongoing, will be reviewed at subsequent visits/contacts. All AEs and SAEs will be followed until resolution, until the condition stabilises, until the event is otherwise explained, or until the participant is lost to follow-up. Once resolved, the adverse event log will be updated. The Investigator will ensure that follow-up includes any supplemental investigations as may be indicated to elucidate the nature and/or causality of the AE or SAE. This may include additional laboratory tests or investigations, histopathological examinations, or consultation with other health care professionals. New or updated information will be recorded on anSAE follow up form, signed and dated by the Investigator. The follow up SAE form should be sent to the Sponsor.

10.1.5 POST-STUDY AES AND SAES

A post-study AE/SAE is defined as any event that occurs outside the AE/SAE detection period. Investigators are not obligated to actively seek AEs or SAEs in former study participants. However, if the Investigator learns of any SAE, including death, at any time after a participants has been discharged from the study, and he/she considers the event reasonably related to the investigational product, the Investigator will promptly notify the Sponsor.

10.2 ADVERSE EVENTS OF SPECIAL INTEREST (AESI)

The AESI listed below will be recorded in more detail via AESI report forms throughout the trial. A template document outlining the information to be recorded will be provided to sites, to be recorded onto Source Data Worksheets or directly into the participants medical records for transcribing into the MACRO eCRF system:

- Ocular surface disease e.g. conjunctivitis/ blepharitis/ keratitis/ dry eye/ keratoconus
- Pain in or around joints
- Facial skin rashes (including acne)

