the comparative effectiveness of systemic therapies is lacking and that "larger, clearly reported, clinically relevant studies are needed to properly compare the benefits of these drugs in adults and children with severe eczema"5. Dupilumab was the first licensed targeted (biologic) therapy for eczema and has a strong evidence base versus placebo but has never been compared with standard systemic therapy^{8,9}. Likewise for the even newer agents tralokinumab, lebrikizumab and JAK inhibitors (abrocitinib, upadacitinib and baricitinib), there is a strong evidence base versus placebo^{10,11}, but there has been no comparison versus standard systemic therapy. There is also minimal available head to head data between the novel agents. Industry led head to head trials have been conducted between JAK inhibitors and dupilumab^{12,13} however the early primary endpoints (as early as 2 weeks) are not optimal given that dupilumab can take 6 months to achieve maximum benefit⁹. A recent network meta-analysis suggested that there is an absence of well powered headto-head trials, that dupilumab and ciclosporin may have better short term effectiveness than methotrexate and that "studies directly comparing established and novel treatments beyond 16 weeks are needed"¹³. Another recent systematic review states "to more directly compare medication efficacy, a standardised controlled trial comparing biologic and non-biologic systemic therapies is needed"14.

Outwith efficacy and effectiveness, the standard and novel systemic therapies confer very different side effect profiles. Whilst the side effects of ciclosporin and methotrexate are well established, those of the more novel agents are less so and of those that we now know about, many were unexpected. Side effects on dupilumab such as ocular surface disease, facial flares and arthritis can affect tolerability for patients. Likewise on JAK inhibitors, infections (including herpes simplex and varicella zoster), acne, blood derangement and rarely venous thrombo-embolism impact patients. Safety is therefore a focus of increasing attention for those prescribing systemic therapies in this context and any informative head-to-head comparative data of the key agents if of clinical utility.

1.1.2 THE COST-EFFECTIVENESS OF SYSTEMIC TREATMENTS USED TO TREAT MODERATE-SEVERE ECZEMA IN ADULTS

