3.2 SECONDARY OBJECTIVES

- 1. Determine the effectiveness of systemic treatments compared with standard of care over 12 months
- 2. Determine the impact on symptoms, quality of life, daily function and mood of systemic treatments compared with standard of care over 12 months
- 3. Determine the safety / tolerability of systemic treatments compared with standard of care, and adherence to the medications over 12 months
- 4. Determine cost-effectiveness of systemic treatments compared with standard of care over 12 months
- 5. Collect data on which first line therapy optimises treatment continuity over the first year and in the event of a treatment switch, which of the tested pathways optimises treatment outcomes at one year.
- 6. Determine the incidence of AEs of special interest (see section 10.2 for further information) on systemic treatments compared with standard of care over 12 months
- 7. Collect clinical data and samples for use by the scientific community to understand atopic eczema disease biology and treatment response in order to improve outcomes in people with atopic eczema.

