1.2.1.1 RENAL IMPAIRMENT

Renal impariment is a frequent and potentially serious complication that can occur during ciclosporin therapy. These functional changes are dose-dependent and are initially reversible, usually responding to dose reduction. During long-term treatment, some patients may develop structural changes in the kidney (e.g. interstitial fibrosis).

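### The list of adverse events of special interest covers dupilumab's three named harms plus acne, but was not extended to the herpes infections and venous thrombo-embolism the protocol names for abrocitinib

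*Protocol*

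**What the plan says.** Protocol section 3.2, objective 6, reads: "Determine the incidence of AEs of special interest (see section 10.2 for further information) on systemic treatments compared with standard of care", over 12 months. Section 4.2 makes AESI safety outcome 6b, beside all adverse events as 6a. Section 10 defines an AESI as a pre-specified event on which fuller information is collected.

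Section 10.2 lists three groups:
- "Ocular surface disease e.g. conjunctivitis/ blepharitis/ keratitis/ dry eye/ keratoconus"
- "Pain in or around joints"
- facial skin rashes, with acne in brackets.

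Section 1.1.1 describes the harms of the two novel classes in consecutive sentences. For dupilumab: "Side effects on dupilumab such as ocular surface disease, facial flares and arthritis can affect tolerability for patients". For abrocitinib's class: "Likewise on JAK inhibitors, infections (including herpes simplex and varicella zoster), acne, blood derangement and rarely venous thrombo-embolism impact patients". Appendix 4 lists herpes simplex (including eczema herpeticum), herpes zoster and acne among abrocitinib's common effects (1.2.1), and venous thrombo-embolism among the uncommon ones (1.2.2).

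**The concern.** Objective 6 reads as a neutral comparison of special-interest harms, each drug against the control. The list that defines it tracks the harms the protocol associates with dupilumab. When abrocitinib became the fourth arm, only acne from its named harms is reflected in the list.

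Followed as written, objective 6 would describe eye, joint and facial skin events in detail for every arm. It would not address the herpes infections and thrombo-embolism that the protocol itself gives as reasons for attention to JAK inhibitors. A reader of the AESI table could take abrocitinib to differ little from ciclosporin apart from acne, when the events most likely to separate them had not been put in the table.

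**Working it through.** No sample size, power or error rate is involved. The check sets the list in section 10.2 against the harms the protocol names.

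**Step 1: the two novel classes, from section 1.1.1.**

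| Named harm | Class | AESI group in 10.2? |
|---|---|---|
| Ocular surface disease | dupilumab | yes |
| Facial flares | dupilumab | yes (facial rashes) |
| Arthritis | dupilumab | yes (joint pain) |
| Herpes simplex | JAK inhibitor | no |
| Varicella zoster | JAK inhibitor | no |
| Acne | JAK inhibitor | yes (within facial rashes) |
| Blood derangement | JAK inhibitor | no |
| Venous thrombo-embolism | JAK inhibitor | no |

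Coverage is 3 of 3 for dupilumab and 1 of 5 for JAK inhibitors. If the two infections are counted as one item, it is 1 of 4. Leaving out blood derangement, which laboratory tests find, 1 of 4 clinically presenting harms is covered; herpes simplex, zoster and venous thrombo-embolism are missing.

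**Step 2: does the protocol show interest in the missing items elsewhere?** Yes. The medical history in section 6.3.3 asks specifically about eye disorders, joint pain, acne needing systemic treatment, and skin infections including herpes simplex and shingles. The first three have a matching AESI group. Herpes and shingles do not.

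**Step 3: where do the missing events go?** Section 10 records all adverse events from consent to the end of study visits. Section 6.5.3 has the log hold dates, severity, seriousness, relatedness to drug and procedure, impact on treatment, and outcome. Section 6.7 sends clinically significant laboratory abnormalities to the same log. So the events are captured, but without the AESI form and outside objective 6.

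**Step 4: which additions could be compared fairly between arms?** Footnotes to Table 1 restrict scheduled post-baseline safety blood pressure and urinalysis to ciclosporin. Safety bloods on ciclosporin fall at weeks 2, 4, 6, 8, 13, 26, 39 and 52 (Appendix 1, 1.4.2.3), which is 8 occasions before any dose increase. On dupilumab from the start they fall at weeks 13, 26 and 52 (Appendix 3, 1.4.2.2), which is 3. Hypertension, renal, cytopenia and hepatic events would be looked for more often in the control arm. Herpes infections and venous thrombo-embolism present clinically and do not depend on that testing.

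**The case against.** The case against is substantial.

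- **An AESI list is meant to be selective.** Section 10 does not define AESI as each drug's main harms. Section 1.1.1 also says that the side effects of ciclosporin and methotrexate are already well known and those of the newer agents less so. This is a fair context for leaving out the older drugs' harms, even though Appendix 1 says: "Renal impariment is a frequent and potentially serious complication that can occur during ciclosporin therapy". This part stands. It does not explain the abrocitinib gap, because the same paragraph treats both novel classes as needing attention.
- **The list is not purely a dupilumab list.** Appendix 2 gives arthralgia and conjunctivitis for methotrexate. Several dupilumab effects in Appendix 3, such as oral herpes, injection-site reactions and angioedema, are not AESIs. This stands as a limit on how the point is worded. It also means a herpes simplex group would be relevant to more than one arm.
- **The events are recorded and can be tabulated by arm.** This stands, and it keeps the point minor.

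A reader might infer that dupilumab is put at a disadvantage by construction, or that the trial's safety conclusion is biased in direction. The documents do not support that. Each group is defined in the same way for every arm, so a higher conjunctivitis rate on dupilumab would be a real difference. The list's composition could mislead only if the groups were pooled into one total, or if AESI stood in for overall safety. The protocol plans neither.

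**Conclusion.** The point holds as an uneven definition of one secondary safety outcome, not as a bias in any stated analysis. Its size is the coverage count: all three dupilumab harms named in section 1.1.1 against one of five for JAK inhibitors. Overall safety under objective 3 and outcome 6a is unaffected.

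This rests on two assumptions. First, sites record herpes infections, zoster and thrombo-embolism in the general log in terms that can be identified later. Second, these events are ascertained similarly across arms. Ciclosporin participants have extra safety contacts, but that caveat applies equally to the three existing groups.

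It is also tempting to conclude that every drug's leading harm, including renal impairment and hypertension on ciclosporin or hepatic events on methotrexate, should become an AESI comparison. That goes too far: with arm-specific testing it would introduce the unequal detection that the present list largely avoids.

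**What to change.** Add three groups to section 10.2: herpes simplex including eczema herpeticum, herpes zoster, and venous thrombo-embolism. Identify cases that occurred before the change from recorded adverse event terms. State that AESI incidence is reported by class.

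If the list is to stay as it is, reword objective 6 to say that it concerns only the three listed event groups and is not a comparison of each drug's characteristic harms.

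If hypertension, renal, cytopenia or hepatic events are considered, attach an explicit caveat that scheduled monitoring differs by arm.

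The cost is an amendment to one list, a few rows on the AESI form, a little more data entry per event, and less detail on events before the change. No visit, test, dose or clinical rule changes.

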10.3 ADVERSE EVENT PROCESSING RESPONSIBILITIES

The Sponsor has delegated the delivery of the Sponsor's responsibility for Pharmacovigilance (as defined in Regulation 5 of the Medicines for Human Use (Clinical Trials) Regulations 2004) to the KHP-CTO.

The KHP-CTO will report SUSARs to the relevant ethics committee and to the MHRA. Reporting timelines are as follows:

- SUSARs which are fatal or life-threatening must be reported not later than 7 days after the sponsor is first aware of the reaction. Any additional relevant information must be reported within a further 8 days;
- SUSARs that are not fatal or life-threatening must be reported within 15 days of the sponsor first becoming aware of the reaction.

The Chief Investigator and King's Health Partners Clinical Trials Office (KHP-CTO) (on behalf of the co-sponsors) will submit a Development Safety Update Report (DSUR) relating to this trial IMP, to the MHRA and REC annually.

The Trial Statistician will report relevant adverse events to the Data Monitoring Committee.

11 ETHICS AND REGULATORY APPROVAL

The KHP-CTO will be responsible for preparing the submission packs for regulatory approval. The CI will be responsible for preparing the submission packs for ethics approval.

Individual participants will consent to participate. The trial will be conducted in compliance with the principles of the Declaration of Helsinki (1996)³⁵, the principles of GCP and in accordance with all applicable regulatory requirements including but not limited to the Research Governance Framework and the Medicines for Human Use (Clinical Trial) Regulations 2004, as amended in 2006 and any subsequent amendments³⁶.

This protocol and related documents will be submitted for review to Health Research Authority (HRA), Research Ethics Committee (REC), and to the Medicines and Healthcare products Regulatory Agency (MHRA) for Clinical Trial Authorisation in the UK.

The Chief Investigator will submit a final report at conclusion of the trial to the KHP-CTO (on behalf of the co-sponsors) and the REC within the timelines defined in the Regulations.

11.1 PROTOCOL AMENDMENTS AND VERSION CONTROL OF STUDY DOCUMENTS

The Trial Manager and the KHP-CTO CRA will be responsible for preparing and submitting protocol amendments to the ethics committee and the MHRA.

Participant-facing documents (e.g. PIS, consent form) will be prepared by the co-ordinating centre and the co-ordinating centre is responsible for maintaining version control.

All correspondence, including submission packs with attachments and approvals, will be filed in the Trial Master File.

Recruiting study sites are responsible for communicating relevant information to participants.

The Trial Manager will be responsible for updating the ISRCTN register subsequent to relevant protocol amendments.

12 STATISTICAL METHODS

12.1 SAMPLE SIZE JUSTIFICATION

This study is designed to test separate pair-wise comparisons of methotrexate, dupilumab and abrocitinib for superiority against ciclosporin. The minimum clinically important difference for EASI is 6.6³⁷. In order to detect a mean absolute difference of 6.6 (assuming a standard deviation of 13.6

(pooled SD=13.6 for EASI at 24 weeks in the pivotal industry trial LIBERTY AD CHRONOS⁹), 20% loss to follow up at primary endpoint, with 90% power and conservative type 1 error rate of 2.5% per comparison) we will need to randomise at least 134 participants per arm. This will have 94% power to test a difference between each comparator and ciclosporin of 6.6 on EASI, 90% for a difference of 6 points, and 80% for 5.2 points. In the subgroup of ~30% participants with severe disease at baseline (n=40 per arm), there is 80% power for a difference of 9.6 points and 50% power for 6.6 points. In order to enable a powered comparison between new arms (e.g. abrocitinib) and the current control arm (ciclosporin) using contemporaneously recruited participants, we will need to extend recruitment to the current control arm.

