12.5 STATISTICAL METHODS FOR PRIMARY AND SECONDARY OUTCOMES

12.5.1 STATISTICAL METHODS FOR PRIMARY OUTCOME

For the repeated measures of the continuous EASI score, linear mixed models will be fitted to the outcome variable at all time points. We will use a linear mixed model, with fixed effects of trial arm, time and a time*arm interaction term, baseline values of the EASI score and minimisation factors (recruitment centre, severity). Random intercepts will be fitted at the participant level.

Marginal treatment effects will be estimated for the EASI score at 6 months and reported as adjusted mean difference in scores between the comparative groups, its standard error, 97.5% confidence intervals and p-value. Significance level (type 1 error) will be two-sided at 0.025.

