17.1 STATISTICAL CONSIDERATIONS

Each additional arm will be considered as a new parallel-group comparison against the nominated standard of care (currently ciclosporin). The advantages of considering these new comparisons in a future platform are multiple:

- a. statistical efficiency from the use of a single control group
- b. operational efficiency from adding a new arm into an existing protocol and database
- c. cost efficiency compared to setting up an independent parallel-group trial

Design considerations for MAMS trials include controlling the type 1 error rate. If the additional trial arms are different, the emphasis should be on controlling the pairwise error rate and powering each research arm separately, as though an independent trial⁴⁷. Therefore, there are no additional considerations for the three-arm trial at this stage, which already has a conservative pairwise adjustment of 0.025. If new arms are added late during the course of this study, there will be little overlap in shared control arm information, which will further reduce the correlation between the pairwise comparisons, and the need to change the type I error for the current arms. However, the timing of new arms will impact on the length of the study required to randomise a concurrent control group with the same eligibility criteria, and we may adjust the randomisation ratio to produce results from each comparison at a similar time.

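### The power figures quoted after the sample size in Protocol 12.1 match a two-sided alpha of 0.05, not the planned 0.025, and are too high

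*Protocol*

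**What the plan says.** Protocol section 12.1 gives the inputs for a pairwise comparison with ciclosporin. The target is set out as "In order to detect a mean absolute difference of 6.6", "assuming a standard deviation of 13.6", with 20% loss to follow-up at the primary endpoint, "with 90% power and conservative type 1 error rate of 2.5% per comparison". The result is at least 134 randomised per arm.

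The same section then reports what that number achieves: "This will have 94% power to test a difference between each comparator and ciclosporin of 6.6 on EASI", with 90% for 6 points and 80% for 5.2 points. For the roughly 30% of participants with severe disease, taken as 40 per arm, it says "there is 80% power for a difference of 9.6 points and 50% power for 6.6 points". No separate alpha, SD or attrition rate is given for these five figures.

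The test level is fixed elsewhere. Section 12.5.1 states "Significance level (type 1 error) will be two-sided at 0.025", with 97.5% confidence intervals. Section 17.1 describes the trial as one "which already has a conservative pairwise adjustment of 0.025".

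**The concern.** The contradiction is visible without calculation. The same number per arm, difference, SD, attrition and alpha are said to give 90% power in one sentence and 94% in the next. If the sample size was computed at 0.025 and the power figures at a looser level, every figure after the first is too favourable.

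The most exposed figures are those for differences below 6.6 points and for severe disease. Section 3.1 places the moderate and severe subgroup analysis within the primary objective, and section 1.2 names severe disease as an evidence gap. The funder and oversight committees rely on section 12.1 to judge what a non-significant result could mean. Figures that are too high invite them to give a null finding more weight than it can bear.

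**Working it through.** **Inputs** (Protocol 12.1 unless noted): difference 6.6; SD 13.6; 20% loss; 134 randomised per arm; severe subgroup 40 randomised per arm (0.30 × 134 = 40.2); two-sided alpha 0.025 (12.5.1); equal allocation (section 2).

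Evaluable per arm after 20% loss: 0.8 × 134 = 107.2, so 107. Severe subgroup: 0.8 × 40 = 32.

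**Step 1. Reproduce the sample size.** The normal approximation is n = 2(z₀.₉₈₇₅ + z₀.₉₀)² × SD² / d² = 2 × (2.241 + 1.282)² × 13.6² / 6.6² ≈ 105.4, so 106. The t-based calculation gives 107, and 107 / 0.8 = 133.75, so 134. The stated number is therefore right at two-sided 0.025. At two-sided 0.05 it would be 113 (normal) or 114 (t).

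**Step 2. Recompute the power figures.** Power is that of a two-sample t-test, using the noncentral t distribution with noncentrality d / (SD × √(2/n)).

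- n = 107: standard error 13.6 × √(2/107) = 1.859. Noncentrality is 3.55, 3.23 and 2.80 for 6.6, 6.0 and 5.2 points. The critical t is 1.97 at alpha 0.05 and 2.26 at 0.025.
- n = 32: standard error 13.6 × √(2/32) = 3.40. Noncentrality is 2.82 and 1.94 for 9.6 and 6.6 points. The critical t is 2.00 at alpha 0.05 and 2.30 at 0.025.

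| Population | Difference | Stated | Alpha 0.05, 20% loss | Alpha 0.025, 20% loss | Alpha 0.025, no loss |
|---|---|---|---|---|---|
| All | 6.6 | 94% | 94.2% | 90.1% | 95.7% |
| All | 6.0 | 90% | 89.5% | 83.3% | 91.2% |
| All | 5.2 | 80% | 79.5% | 70.5% | 80.9% |
| Severe | 9.6 | 80% | 79.4% | 70.0% | 80.6% |
| Severe | 6.6 | 50% | 48.1% | 36.7% | 45.8% |

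The no-loss column uses 134 and 40 analysed per arm. Only alpha 0.05 with 20% loss matches all five stated figures within 2 points. The normal approximation leads to the same conclusion: 94.4, 89.7, 79.9, 80.6 and 49.3% at alpha 0.05, against 90.5, 83.8, 71.1, 72.0 and 38.2% at 0.025.

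**Step 3. Detectable differences at two-sided 0.025.** Differences with 80% power are 5.8 points overall (5.77 by t, 5.73 by normal approximation) and 10.7 points in the severe subgroup (10.5 by normal approximation). The protocol gives 5.2 and 9.6.

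**Step 4. Can the 50% subgroup figure be reached at 0.025?** It needs 44 evaluable per arm by t, since 43 gives 49.0% and 44 gives 50.1%. That exceeds the 40 randomised, so under the stated SD it is out of reach even with no loss.

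**The case against.** Four points can be made for the plan.

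- **The design figure is correct.** 134 per arm does give 90% for 6.6 points at two-sided 0.025, and the outcome, alpha and analysis model are untouched. This stands, and it confines the error to the descriptive power figures.
- **The planned model adjusts for baseline EASI** (section 12.5.1), which may raise power above an unadjusted t-test. The protocol states no correlation, so this can only be shown as a range. At 0.025 with 107 per arm, an assumed correlation of 0.3 gives 93, 87 and 75% for 6.6, 6.0 and 5.2 points; 0.4 gives 95, 90 and 79%; 0.5 gives 97, 93 and 83%. In the severe subgroup 0.4 gives 78 and 43%, and 0.5 gives 83 and 48%. Actual power could thus approach the stated values, but section 12.1 claims no such adjustment, and no single value in this range reproduces all five figures.
- **The cause is inferred.** The power sentences name no alpha. Two-sided 0.05 equals one-sided 0.025 numerically, and "conservative type 1 error rate of 2.5% per comparison" in section 12.1 gives no sidedness. Section 12.5.1 settles that as two-sided. Ignoring attrition at 0.025 comes close on four of the five figures, but it drops the 20% loss stated one sentence earlier and gives 46% where the plan says 50%. Alpha 0.05 is the best explanation, not a proven one. The contradiction does not depend on it.
- **Confidence intervals will be reported**, and the protocol admits only 50% power for 6.6 points in severe disease. Both limit misreading of a null result, but neither makes the stated power correct.

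**Conclusion.** The concern holds. Under the protocol's own inputs, the secondary power figures are too high by about 4, 7 and 9 percentage points overall (94 against 90.1, 90 against 83.3, 80 against 70.5). In the severe subgroup they are too high by about 10 and 13 points (80 against 70.0, 50 against 36.7). At 5.2 points the type 2 error is about 29% (100 − 70.5), not 20%.

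These values rest on an unadjusted two-sample t-test with SD 13.6, 20% loss and two-sided alpha 0.025. Lower loss or a useful baseline correlation would raise actual power, so the finding is that the figures are misstated, not that the trial must deliver less. The sample size of 134 per arm is unaffected.

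**What to change.** Replace the two power sentences in section 12.1 with figures at two-sided 0.025 after 20% loss, naming the method as an unadjusted two-sample t-test with SD 13.6:

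- **Overall (134 randomised, 107 evaluable per arm):** 90% for 6.6 points, 83% for 6.0, 71% for 5.2, and 80% for 5.8.
- **Severe subgroup (40 randomised, 32 evaluable per arm):** 70% for 9.6 points, 37% for 6.6, and 80% for 10.7.

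If the sponsor intends the present figures to reflect other assumptions, such as adjustment for baseline, the section should state those assumptions, including the correlation used, and show that they reproduce the numbers at 0.025. The sample size and the analysis need no change. The cost is a wording amendment to the protocol and less favourable stated power.
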